4.5.6 Laboratory, Biomarker, and Other Biological Samples

Assessments that require blood draws should be monitored closely to ensure that institutional guidance regarding total blood volume taken for samples is maintained. In situations where no institutional guidance is available, no more than 2.5% of the total blood volume should be taken at one time and no more than 5% of the total blood volume should be taken over a 30-day period (total blood volume is defined as 80 mL/kg). Institutions should use micro-sampling systems to minimize the amount of blood drawn when able. In situations where the total amount will exceed the amount stated above, clinical laboratory assessments should be prioritized. Any remaining blood should be sent for PK analysis and immunogenicity followed by biomarker and PD analyses.

Laboratory tests results must meet the inclusion criteria and not meet the exclusion criteria at the time of screening. If laboratory tests are performed again prior to the first dose, they must continue to meet the inclusion criteria and not meet the exclusion criteria.

Samples for the following laboratory tests will be sent to the study site's local laboratory for analysis:

- Hematology (WBC count, hemoglobin, platelet count, 3-cell differential count [absolute neutrophils, monocytes, and lymphocytes])
- Serum chemistry (sodium, potassium, magnesium, chloride, bicarbonate, glucose, BUN or urea, creatinine, total protein, albumin, phosphorus, calcium, total bilirubin [if abnormal, fractionate sample for direct and indirect], alkaline phosphatase, ALT, AST, LDH, amylase, and lipase)
- Creatinine clearance should be done as clinically indicated. If radioisotope glomerular filtration rate is routinely performed at the institution to measure patients' creatinine clearance, this test can be used to assess renal function at screening, per the eligibility criteria. Otherwise, serum creatinine is sufficient to document renal function at screening.
- Coagulation panel (INR, aPTT, PT)
- Urinalysis (specific gravity, glucose, protein, blood) in children who are >3 years of age
- Pregnancy test

All patients of childbearing potential will undergo a serum pregnancy test at screening (prior to Cycle 1) within 1 week prior to initial dose. Urine or serum pregnancy test will be performed prior to all subsequent cycles.

- Thyroid function testing (thyroid-stimulating hormone, free T3, free T4)
- Viral serology at screening (hepatitis B surface antigen, hepatitis B surface antibody, total hepatitis B core antibody, hepatitis C antibody, human immunodeficiency virus (HIV)-1, and HIV-2 antibody)

If a patient is positive for hepatitis B core antibody at screening, a test for hepatitis B virus DNA should be performed prior to Day 1 of Cycle 1.

If a patient is positive for hepatitis C antibody at screening, a test for hepatitis C virus RNA should be performed prior to Day 1 of Cycle 1.

The following samples will be sent to a central laboratory or the Sponsor or selected designee for analysis:

- Archival or fresh primary tumor tissue samples for exploratory research on candidate biomarkers, including but not limited to PD-L1, PD-1, and CD8

For patients with archival samples: Representative formalin-fixed paraffin-embedded (FFPE) tumor specimens in paraffin blocks or at least 15 freshly cut, unstained, serial slides (blocks preferred), with an associated pathology report, are required for study entry. The specimen should be of good tissue quality and have sufficient viable tumor content as determined by the institutional pathologist. Patients with fewer than 15 slides available may be eligible for study entry following discussion with the Medical Monitor. The tumor specimen and associated pathology report must be confirmed to be available prior to patient participation in any study-specific screening procedures and must be shipped within 30 days of first dosing.

Patients will be encouraged to submit all available FFPE tumor specimens from prior surgeries and biopsies performed as part of routine medical care. If a patient has multiple archival specimens available but wants to submit only one sample, the specimen obtained closest to the start of treatment should be used.

Patients without archival samples must undergo a core or excisional biopsy prior to enrollment. Fine-needle aspiration, brush biopsy, and lavage samples are not acceptable. *Submission of bone biopsy specimens is strongly discouraged because of complications in the assessment of such tissue. These specimens can be used only if no other tissue is available.*

Unused archival tumor blocks will be returned to the sites at the end of the study or upon site request.

- PK assay

Serum samples will be assayed for atezolizumab concentration with use of a validated immunoassay. Any residual PK samples can be used for additional ATA testing if needed.

- ATA assays

Serum samples will be assayed for the presence of ATAs to atezolizumab with use of a validated immunoassay.

- In children who have been vaccinated, tetanus toxoid IgG antibody titers
- Plasma samples for exploratory research on candidate biomarkers, including but not limited to the following: cytokines (e.g., IL-2 and IFN- γ), ctDNA concentration, ctDNA mutations (e.g., *KRAS*, *P53*, *PTEN*)
- Whole blood samples for analysis of immune cell expression of biomarkers, including but not limited to the following: PD-L1, CD4, CD8, FoxP3, IFN- γ

- A whole blood sample for molecular analysis of mutations and single-nucleotide polymorphisms (SNPs) is required ONLY for patients who consent to submitting optional on-study tissue (tissue submission described in Section 4.5.7). This sample may be used for the analysis of novel mutations detected in tumor tissue in order to verify the somatic nature of this mutation and SNPs that might be associated with safety, efficacy, or pharmacokinetics of the drug.
- Whole blood samples for TBNK cell enumeration

Serum samples will be obtained at baseline and held for possible testing in patients who develop immune-related or inflammatory adverse events during the study. The samples will be analyzed as needed to determine baseline values for the following:

- Auto-antibody testing
 - Anti-nuclear antibody
 - Anti-double-stranded DNA
 - Circulating anti-neutrophil cytoplasmic antibody
 - Perinuclear anti-neutrophil cytoplasmic antibody

For sampling procedures, storage conditions, and shipment instructions, see the Laboratory Manual.

Samples will be destroyed when the final Clinical Study Report has been completed, with the following exceptions:

- Any remaining samples collected for pharmacokinetics, biomarker assays, and ATA assays may be used for exploratory biomarker profiling, identification, and PD assay development purposes and for additional safety assessments (e.g., ATA assay) as appropriate. *These samples will be destroyed no later than 5 years after the final Clinical Study Report has been completed.* The remainder of samples obtained for study-related procedures will be destroyed no later than 5 years after the date of final closure of the clinical database unless the patient gives specific consent for the remainder of the samples to be stored for optional exploratory research. If the patient provides consent for optional exploratory research, the samples will be destroyed no later than 15 years after the date of final closure of the clinical database.

4.5.7 Samples for Roche Clinical Repository

4.5.7.1 Overview of the Roche Clinical Repository

The Roche Clinical Repository (RCR) is a centrally administered group of facilities used for the long-term storage of human biologic specimens, including body fluids, solid tissues, and derivatives thereof (e.g., DNA, RNA, proteins, peptides). The collection and analysis of RCR specimens will facilitate the rational design of new pharmaceutical agents and the development of diagnostic tests, which may allow for individualized drug therapy for patients in the future.

Specimens for the RCR will be collected from patients who give specific consent to participate in this optional research. RCR specimens will be used to achieve the following objectives:

- To study the association of biomarkers with efficacy, adverse events, or progressive disease
- To increase knowledge and understanding of disease biology
- To study drug response, including drug effects and the processes of drug absorption and disposition
- To develop biomarker or diagnostic assays and establish the performance characteristics of these assays

4.5.7.2 Approval by the Institutional Review Board or Ethics Committee

Collection and submission of biological samples to the RCR is contingent upon the review and approval of the exploratory research and the RCR portion of the Informed Consent Form by each site's Institutional Review Board (IRB) or Ethics Committee (EC) and, if applicable, an appropriate regulatory body. If a site has not been granted approval for RCR sampling, this section of the protocol (Section 4.5.7) will not be applicable at that site.

4.5.7.3 Sample Collection

The following samples will be collected for research purposes, including but not limited to research on dynamic (non-inherited) biomarkers related to atezolizumab or solid tumors:

- Fresh tissue from study biopsies and residual tissue from non-study-related procedures, will be collected from the primary tumor location, metastatic site, or site of local recurrence or advancement for analyses that may include DNA or RNA extraction. Samples should be obtained at the following timepoints: prior to drug initiation, 4–6 weeks after the first dose of drug, and at the time of progressive disease (if applicable). Patient may choose to consent to any or all of these timepoints.

A minimum of three fresh tissue cores should be acquired using an 18-gauge needle. If not feasible, one or two cores may be acceptable after discussion with the Medical Monitor.

Patients consenting to the optional study biopsy will also be required to provide a mandatory whole blood sample listed under the main protocol (Section 4.5.6).

For all samples, dates of consent should be recorded on the associated RCR page of the eCRF. For sampling procedures, storage conditions, and shipment instructions, see the Laboratory Manual.

RCR specimens will be destroyed no later than 15 years after the date of final closure of the associated clinical database. The RCR storage period will be in accordance with the IRB/EC-approved Informed Consent Form and applicable laws (e.g., health authority requirements).

The dynamic biomarker specimens will be subject to the confidentiality standards described in Section 8.4.

4.5.7.4 Confidentiality

Data generated from RCR specimens must be available for inspection upon request by representatives of national and local health authorities and Roche monitors, representatives, and collaborators, as appropriate.

Patient medical information associated with RCR specimens is confidential and may be disclosed to third parties only as permitted by the Informed Consent Form (or separate authorization for use and disclosure of personal health information) signed by the patient, unless permitted or required by law.

Data derived from RCR specimen analysis on individual patients will generally not be provided to study investigators unless a request for research use is granted. The aggregate results of any research conducted using RCR specimens will be available in accordance with the effective Roche policy on study data publication.

Any inventions and resulting patents, improvements, and/or know-how originating from the use of the RCR data will become and remain the exclusive and unburdened property of Roche, except where agreed otherwise.

4.5.7.5 Consent to Participate in the Roche Clinical Repository

The Informed Consent Form will contain a separate section that addresses participation in the RCR. The investigator or authorized designee will explain to each patient the objectives, methods, and potential hazards of participation in the RCR. Patients will be told that they are free to refuse to participate and may withdraw their specimens at any time and for any reason during the storage period. A separate, specific signature will be required to document a patient's agreement to provide optional RCR specimens. Patients who decline to participate will not provide a separate signature.

The investigator should document whether or not the patient has given consent to participate by completing the RCR Research Sample Informed Consent eCRF.

In the event of an RCR participant's death or loss of competence, the participant's specimens and data will continue to be used as part of the RCR research.

4.5.7.6 Withdrawal from the Roche Clinical Repository

Patients who give consent to provide RCR specimens have the right to withdraw their specimens from the RCR at any time for any reason. If a patient wants to withdraw consent to the testing of his or her specimens, the investigator must inform the Medical Monitor in writing of the patient's wishes through use of the RCR Subject Withdrawal Form and, if the study is ongoing, must enter the date of withdrawal on the RCR Research Sample Withdrawal of Informed Consent eCRF. The patient will be provided with instructions on how to withdraw consent after the study is closed. A patient's withdrawal from Study GO29664 does not, by itself, constitute withdrawal of specimens from the RCR. Likewise, a patient's withdrawal from the RCR does not constitute withdrawal from Study GO29664.

4.5.7.7 Monitoring and Oversight

RCR specimens will be tracked in a manner consistent with Good Clinical Practice by a quality-controlled, auditable, and appropriately validated laboratory information management system, to ensure compliance with data confidentiality as well as adherence to authorized use of specimens as specified in this protocol and in the Informed Consent Form. Roche monitors and auditors will have direct access to appropriate parts of records relating to patient participation in the RCR for the purposes of verifying the data provided to Roche. The site will permit monitoring, audits, IRB/EC review, and health authority inspections by providing direct access to source data and documents related to the RCR samples.

4.6 PATIENT, TREATMENT, STUDY, AND SITE DISCONTINUATION

4.6.1 Patient Discontinuation

Patients have the right to voluntarily withdraw from the study (or be withdrawn by their patients or caregivers, if the patient is a minor) at any time for any reason. In addition, the investigator has the right to withdraw a patient from the study treatment at any time. Reasons for withdrawal from the study may include but are not limited to the following:

- Patient withdrawal of consent (or withdrawal of consent by their patients or caregivers, if the patient is a minor) at any time
- Any medical condition that the investigator or Sponsor determines may jeopardize the patient's safety if he or she continues in the study
- Investigator or Sponsor determines it is in the best interest of the patient.
- Patient non-compliance with the study procedures (e.g., dosing instructions, study visits)

Every effort should be made to obtain information on patients who withdraw from the study. The primary reason for withdrawal from the study should be documented on the appropriate eCRF. *In situations where it is either unsafe or not in the best interest of the patient to complete follow-up assessments after study drug discontinuation, survival data only may be submitted during the follow-up period with approval of the*

Medical Monitor. Patients will not be followed up for any reason after consent has been withdrawn. Patients who withdraw from the study will not be replaced.

4.6.2 Study Drug Discontinuation

Patients must discontinue study drug if they experience any of the following:

- Symptomatic deterioration attributed to disease progression as determined by the investigator after integrated assessment of radiographic data, biopsy results, and clinical status
- Unacceptable toxicity despite per-protocol treatment interruptions
- Pregnancy
- Withdrawal of consent
- Interruption of study treatment for >105 days (*e.g., more than 105 days between infusions*) because of an atezolizumab-related adverse event, except in patients who must be tapered off corticosteroids used to treat adverse events (see Section 5.1.1.1 for details). This duration may be extended after consultation with the Medical Monitor.

Patients who discontinue study drug for any reason will be asked to return to the clinic for a study drug discontinuation visit and undergo follow-up assessments (see the schedule of assessments in [Appendix 1](#)). If treatment with another anti-cancer treatment is scheduled to begin within 90 days after the last dose of atezolizumab, assessments at this visit should be performed before the patient starts the other treatment, if possible. Patients who discontinue for reasons other than progressive disease should continue follow-up assessments, including tumor assessments, using the long-term follow-up schedule (*e.g., every 3 months for the first 2 years, every 6 months during Year 3, etc.*) until radiographic documentation of progressive disease, they start another treatment, or consent is withdrawn. For patients who continue receiving study drug beyond radiographic progressive disease, assessments should be continued until they stop taking study drug. The primary reason for study drug discontinuation should be documented on the appropriate eCRF.

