PFS is defined as the time from initiation of study drug to the first documented occurrence of disease progression, as determined by the investigator using RECIST v1.1 for patients with solid tumors (see [Appendix 6](#)), *mINRC* for patients with neuroblastoma (see [Appendix 3](#)), Revised Response Criteria for Malignant Lymphoma for patients with Hodgkin's lymphoma or non-Hodgkin's lymphoma (see [Appendix 4](#)), and *RANO criteria* (see [Appendix 11](#)) for patients with ATRT, or death from any cause, whichever occurs first. Data for patients without progressive disease or death will be censored at the date of the last tumor assessment at which the patient was known to be progression-free or, if no tumor assessment is performed after the baseline visit, at the date of initiation of study drug. The Kaplan-Meier approach will be used to estimate median PFS. The 95% CI of the median PFS will be estimated using the Brookmeyer

and Crowley method. Subgroup analysis of PFS by tumor type cohort will be conducted as appropriate.

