6.6.2 Secondary Efficacy Endpoints

The secondary efficacy endpoints include DOR and OS.

For patients who achieve an objective response, DOR is defined as the time from the first tumor assessment that supports the patient's objective response to the time of progressive disease, as determined by the investigator using *mINRC* for patients with neuroblastoma (see [Appendix 3](#)), Revised Response Criteria for Malignant Lymphoma for patients with Hodgkin's lymphoma or non-Hodgkin's lymphoma (see [Appendix 4](#)), *RANO criteria* (see [Appendix 11](#)) for patients with ATRT, and RECIST v1.1 for patients with other solid tumors (see [Appendix 6](#)), or death from any cause, whichever occurs first. The censoring method for DOR will be the same as that for PFS. The Kaplan-Meier approach will be used to estimate median DOR. The 95% CI of the median DOR will be estimated using the Brookmeyer and Crowley method. Subgroup analysis of DOR by tumor type cohort will be conducted as appropriate.

OS is defined as the time from initiation of study drug to death from any cause. Patients who are alive at the data cutoff date will be censored at the date the patient was last known to be alive. Patients with no post-baseline information will be censored at the date of initiation of study drug. The Kaplan-Meier approach will be used to estimate median OS. The 95% CI of the median OS will be estimated using the Brookmeyer and Crowley method. Subgroup analysis of OS by tumor type cohort will be conducted as appropriate.

In addition, analyses for ORR, PFS, and DOR using irRC for patients with neuroblastoma, Hodgkin's lymphoma or non-Hodgkin's lymphoma, and immune-modified RECIST v1.1 for patients with other solid tumors will be conducted with the same approaches as explained above.

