- ^u Collect sample between 90 to 150 days after last dose of study drug.
- ^v The same *imaging technique(s) and procedure(s)* (CT, MRI, FDG-PET, *and/or* MIBG scan) used to assess disease sites at screening should be used throughout the study (e.g., the same contrast protocol for CT scans). To the extent that is feasible, assessments should be performed by the same evaluator to ensure internal consistency across visits. See Section 4.5.5 for detailed information on tumor and response evaluations.
- ^w Tumor assessments must be performed during the last week of Cycles 2, 4, 6, and 8 and every 4th cycle thereafter (i.e., within 7 days prior to Day 1 of the next cycle). At the investigator's discretion, tumor assessments may be repeated at any time if progressive disease is suspected. An objective response should be confirmed by repeat assessments ≥ 4 weeks after initial documentation. Patients who discontinue study drug without progressive disease should continue follow up assessments, including tumor assessments, using the long-term follow up schedule (e.g., every three months for the first 2 years, every 6 months during year 3, etc.) until radiographic documentation of progressive disease, they start another treatment or consent is withdrawn. Patients who continue to receive study drug beyond radiographic progressive disease should continue follow-up assessments until they stop taking study drug.

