diameter normally used by radiologists to judge if a node is involved by solid tumor. Nodal size is normally reported as two dimensions in the plane in which the image is obtained (for CT, this is almost always the axial plane; for MRI, the plane of acquisition may be axial, sagittal, or coronal). The smaller of these measures is the short axis. For example, an abdominal node that is reported as being 20 mm \times 30 mm has a short axis of 20 mm and qualifies as a malignant, measurable node. In this example, 20 mm should be recorded as the node measurement. All other pathological nodes (those with short axis ≥ 10 mm but < 15 mm) should be considered non-target lesions. Nodes that have a short axis of < 10 mm are considered non-pathological and should not be recorded or followed.

Lesions irradiated within 3 weeks prior to Cycle 1 Day 1 may not be counted as target lesions.

Non-Target Lesions

All other lesions (or sites of disease), including pathological lymph nodes, should be identified as non-target lesions and should also be recorded at baseline. Measurements are not required.

It is possible to record multiple non-target lesions involving the same organ as a single item on the eCRF (e.g., “multiple enlarged pelvic lymph nodes” or “multiple liver metastases”).

After baseline, changes in non-target lesions will contribute only in the assessment of complete response (i.e., a complete response is attained only with the complete disappearance of all tumor lesions, including non-target lesions) and will not be used to assess progressive disease.

New Lesions

During the study, all new lesions identified and recorded after baseline must be assessed at all tumor assessment timepoints. New lesions will also be evaluated for measurability with use of the same criteria applied to prospective target lesions at baseline per RECIST, (e.g., non-lymph node lesions must be ≥ 10 mm; see note for new lymph node lesions below). Up to a maximum of five new lesions total (and a maximum of two lesions per organ), all with measurements at all timepoints, can be included in the

Appendix 5

Modified Response Evaluation Criteria in Solid Tumors (cont.)

tumor response evaluation. New lesion types that would not qualify as target lesions per RECIST cannot be included in the tumor response evaluation.

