The appearance of new lymph nodes with diameter < 10 mm should not be considered pathological and not considered a new lesion.

B.3 RESPONSE CRITERIA

Timepoint Response

It is assumed that at each protocol-specified timepoint, a response assessment occurs. [Table 1](#) provides a summary of the overall response status calculation at each timepoint for patients who have measurable disease at baseline.

Complete Response (CR): Disappearance of all target and non-target lesions. Lymph nodes that shrink to < 10 mm short axis are considered normal.

Partial Response (PR): At least a 30% decrease in the sum of the diameters of all target and all new measurable lesions, taking as reference the baseline sum of diameters, in the absence of CR.

Note: the appearance of new measurable lesions is factored into the overall tumor burden, but *does not automatically qualify as progressive disease* until the sum of the diameters increases by $\geq 20\%$ when compared with the sum of the diameters at nadir.

Stable Disease (SD): Neither sufficient shrinkage to qualify for PR nor sufficient increase to qualify for PD, taking as reference the smallest sum of the diameters while on study.

Progressive Disease (PD): At least a 20% increase in the sum of diameters of all target and selected new measurable lesions, taking as reference the smallest sum on study (nadir SLD; this includes the baseline sum if that is the smallest on study). In addition to the relative increase of 20%, the sum must also demonstrate an absolute increase of at least 5 mm.

Impact of New Lesions on Modified RECIST

New lesions alone do not qualify as progressive disease. However, their contribution to total tumor burden is included in the sum of the diameters, which is used to determine the overall modified RECIST tumor response.

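### Tumor scans may end at conventional progression, but immune-modified PFS and DOR need a later, differently defined progression; these secondary endpoints are expected to be biased upward and need a companion analysis

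*Combined protocol and SAP*

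**What the plan says.** - **Who is scanned after drug stops.** Section 4.6.2: "Patients who discontinue for reasons other than progressive disease should continue follow-up assessments, including tumor assessments, using the long-term follow-up schedule". This continues "until radiographic documentation of progressive disease, they start another treatment, or consent is withdrawn". For the others: "For patients who continue receiving study drug beyond radiographic progressive disease, assessments should be continued until they stop taking study drug". Appendix 1, footnote w, repeats the rule: "Patients who continue to receive study drug beyond radiographic progressive disease should continue follow-up assessments until they stop taking study drug".
- **Which progression.** Section 4.6.2 does not name the criteria. Section 4.5.5.2 sets RECIST v1.1 as the standard, with tumor-specific conventional criteria for neuroblastoma, lymphoma and ATRT. Under RECIST v1.1 (Appendix 6), a new lesion or unequivocal non-target progression is progression.
- **Modified RECIST (Appendix 5).** "New lesions alone do not qualify as progressive disease". Changes in non-target lesions "will not be used to assess progressive disease". Measurable new lesions are added to the sum of diameters, and progression requires that sum to rise by at least 20% and 5 mm from nadir.
- **irRC (Appendix 7), for neuroblastoma and lymphoma.** Progression must be confirmed by a consecutive assessment at least 4 weeks later.
- **Analysis.** In Section 6.6.1 a PFS event is progression or death; patients with neither "will be censored at the date of the last tumor assessment at which the patient was known to be progression-free". DOR is censored the same way. Section 6.6.2 adds that analyses using irRC and "immune-modified RECIST v1.1 for patients with other solid tumors will be conducted with the same approaches as explained above".

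**The concern.** The scan-stopping rule follows one definition of progression and the endpoint uses another. A patient who stops drug because of, say, non-target progression has not progressed by modified RECIST at that scan, and no further scan is required. A patient with neuroblastoma or lymphoma who stops at first progression, with no later scan, cannot reach confirmed immune-related progression however much the tumor has grown. A patient treated beyond progression has the same gap from the day drug stops.

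The loss of scans is linked to prognosis by the protocol's own rules. Staying on drug past progression requires clinical benefit, no signs of unequivocal progression and no performance decline due to progression (Section 4.5.5.2), and those patients must be rescanned after 2 cycles (Section 4.5.5.1). Symptomatic deterioration obliges the patient to stop (Section 4.6.2). Likely pseudoprogressors therefore tend to keep their scans and failing patients to lose them. Conventional and immune-modified PFS will both be reported, and a reader could not tell benefit beyond RECIST from scans that simply stopped. No planned sensitivity analysis addresses this.

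**Working it through.** The plan gives no expected value, event count or power for immune-modified PFS or DOR, so there is no figure to reproduce. The check follows one patient through the rules, then sizes the effect under stated assumptions.

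**Step 1. One patient.** Conventional progression at scan date c, caused only by a non-target lesion; drug stops.
- Conventional PFS: event at c.
- Modified RECIST: no progression at c, and no later scan required.
- Sections 6.6.1 and 6.6.2: censored at c if alive, otherwise an event at death.
- Full scanning would give an event at modified progression or death, whichever came first.

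The tumor assessment marked in Appendix 1 at the discontinuation visit does not close the gap, because footnote c allows that visit to be the one where progression is first noted.

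**Step 2. The right comparison.** Bias = modified PFS under the protocol rule minus modified PFS with scans continued to modified progression. Both terms use the same endpoint; conventional PFS is not the reference.

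**Step 3. Six-month PFS, 36 main scenarios** (200,000 simulated patients each).
- From the documents: scans at weeks 6, 12, 18 and 24, then every 12 weeks (Section 4.5.5.1: Cycles 2, 4, 6, 8, then every 4th 3-week cycle). Follow-up runs from 6 months (Section 3.2) to 42 months (6 plus about 36 months of accrual, Section 3.1.1).
- Assumed: median conventional PFS 1.5 or 3 months; 20, 40 or 60% of progressions conventional-only; mean lag to modified progression 1 or 2 months, counted from the underlying conventional progression; mean survival after progression 4, 8 or 12 months; 80% stop drug at progression.

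| Median conventional PFS | Conventional-only share | Mean lag | Mean survival after progression | Full scanning | Protocol rule | Difference |
|---|---|---|---|---|---|---|
| 3 mo | 20% | 1 mo | 4 mo | 28.9% | 30.5% | +1.6 (smallest of 36) |
| 3 mo | 40% | 2 mo | 8 mo | 33.2% | 38.5% | +5.3 |
| 1.5 mo | 60% | 2 mo | 12 mo | 16.1% | 28.0% | +11.9 (largest of 36) |
| 3 mo | 40% | 24 mo | 24 mo | 49.7% | 48.9% | -0.8 (extra pseudoprogression case) |

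Across the 36, about 6 to 31% of all patients lose scans before modified progression, and 73 to 95% of those still enter as events, at death. At a 40% share the difference is 3.2 points (29.9% to 33.1%) to 7.7 points (13.4% to 21.1%). The median is unchanged in 28 of 36 and rises by at most about 1.4 months (4.14 to 5.52) in the other 8.

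**Step 4. A harsher convention.** The lag is counted from the scan that shows conventional progression, so no conventional-only patient has modified progression at that scan. Assumed: true median progression 45 or 75 days; share 30-50%; 80-100% stopping; median survival after progression 120-240 days; follow-up 6-24 months; lag from a mean of 30 days up to a median of 60 days (mean 60/0.693 = 87 days). Six-month modified PFS is about 4 to 21 points too high.

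**Step 5. What the median shows.** True median 75 days, everyone stopping at progression:
- Conventional median: 84 days.
- 30% share: protocol rule 126, full scanning about 126 (121-126 in one rerun). The 42-day gap from 84 is nearly all definition and scan grid.
- 50% share: protocol rule 165-168, full scanning 126. Of the 81-84 days above 84, 42 are definition and grid and 39-42 are bias.

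DOR was not simulated.

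**The case against.** Several stronger readings are tempting and are not supported.

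- **That the bias always favors the drug.** The plan does not guarantee it. If most patients who stop have pseudoprogression and a long course, the shift can vanish or reverse, as in the last table row. That row assumes a mean of 24 months to both modified progression and death, which is unlikely for patients stopping at progression, but it shows the direction is an inference.
- **That modified RECIST ignores new lesions.** A measurable new lesion enters the sum and can produce modified progression at the same scan. The gap is limited to non-target progression, non-measurable new lesions, and measurable new lesions that leave the sum below threshold.
- **That these patients are counted as progression-free.** They are censored at the last scan, and death remains an event; survival assessment continues in follow-up. Much of the error is a late event date.
- **That the excess of the immune-modified over the conventional median is the bias.** Modified progression is later by definition; Step 5 separates the two parts.

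It is also fair that radiographic progression is not itself a mandatory reason to stop, so having everyone stop is a worst case; that no formal testing is planned (Section 6.1); that cohort expansion rests on responder counts; and that no comparison of immune-modified with conventional PFS is specified. These points limit the consequence. They do not remove the mismatch, which is in the text and has no handling rule.

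**Conclusion.** The point holds in a limited form. For patients who stop drug at a conventional-only or unconfirmed progression, or after treatment beyond progression, required scanning ends before the immune-modified endpoint is settled, and the censoring is probably informative. Immune-modified RECIST and irRC PFS and DOR are expected to be biased upward.

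The size rests on inputs the documents do not give: the conventional-only share, the proportion stopping at progression, the lag and later survival. The 4 to 21 points belong to the harsher convention of Step 4, so 4 is not a floor; Step 3 gives 1.6 to 11.9 points. The 6-month rate shows the bias better than the median, which jumps between scan dates. For DOR the argument is structural only. Primary ORR and primary PFS use conventional criteria and are untouched, so this is a worthwhile repair to secondary endpoints and does not threaten the main conclusions.

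**What to change.** In Section 6.6.2, prespecify a companion (sensitivity) analysis for PFS and DOR under both immune-modified RECIST and irRC: a patient with conventional progression and no later tumor assessment before stopping drug or starting new therapy has an event on the date of conventional progression. Patients with a later scan that shows no immune-modified progression carry on past that date. Report it beside the analysis under the Section 6.6.1 rules, give 6-month rates as well as medians, and state how many patients the rule changes. Count separately those who stop after treatment beyond progression, because the rule does not reclassify them once they have a later scan.

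It should not replace the planned analysis. True pseudoprogressions without a later scan become events, so it can understate immune-modified PFS; in a rerun it fell below full scanning when used alone. The two results serve as a practical bracket, not as strict bounds, since the planned analysis can itself fall slightly low when pseudoprogression dominates.

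Cost: a short SAP addition and some programming, with no extra scans. Continuing scans to immune-modified progression would address the gap directly, but needs a protocol amendment and imaging of patients who have stopped drug.
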